1.1 Background/rationale

To improve care for patients with sepsis, comply with national financial incentive programmes, and make best use of the introduction of electronic health records hospitals in England have introduced digital sepsis alerts. A variety of algorithms have been used, with different workflows and with different implementation strategies.

A variety of studies have demonstrated that digital sepsis alerts, and more general deteriorating early warning scores such as NEWS2, have high predictive power for mortality.[1] A small number of studies have shown that introducing digital alerts to identify patients at risk of deterioration have had an impact on patient outcomes.[2-3]

Although randomised control trials are considered the gold standard for evidence, digital alerts have generally been introduced across hospitals without randomisation or phased across the hospital. In ICHT sepsis alerts were introduced in a phased approach and we used a propensity score based causal inference method (inverse probability of treatment weighting), common in the analysis of natural experiments, to emulate as much as possible a RCT using real world healthcare data. In ICHT the introduction of digital sepsis alerts was associated with a 23% lower risk of death within 30 days.[4]

In this study we aim to analyse the impact of the introduction digital alerts across five NHS Trusts. With the exception of ICHT the introduction of alerts was part of the introduction of electronic health records (EHR). This presents challenges, for example:

- Data availability prior to the introduction of EHRs is limited to data routinely collected for administrative purposes. This includes admission, discharge and formal diagnosis information, but excludes detailed microbiology information and detailed patient treatment information such as the administration of antibiotics.
- The impact of the alerts on patient outcomes will be confounded by the introduction of EHRs, a major change in the hospital system.

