Although we would expect digital sepsis alerts to have the main impact on patients with sepsis, and this is the stated aim of many commercial sepsis alerts, administrative data may not be sufficient to identify patients with sepsis, particularly as national guidance on sepsis coding changed in 2014, effectively increasing the number of patients with an official diagnosis of sepsis.[5] In addition, efficient clinical response to digital sepsis alerts may result in a decrease in disease progression to sepsis. We have therefore decided to focus on outcomes of patients with an ICD-10 Suspicion of Sepsis code.[6] We will use interrupted time series with a control to determine the impact of the introduction of alerts on patient outcomes and process measures. Interrupted time series is an important methodology which allows

before and after comparisons whilst taking trends prior to the intervention into account and is considered a robust methodology for analysing natural experiments. However, confounding due to other 'interventions' occurring at the same time as the intervention of interest can confound interpretation. A control is an appropriate method to take this type of confounding into account.[7]

For the control we have selected patients with an ICD-10 code included in the category gastrointestinal bleeding. This is a suitable control as we would not expect these patients to trigger a sepsis alert and outcomes should not be impacted by patients being identified as having sepsis. The ICD-10 codes included in this indicator are shown in Table 1.

Objective - Quantify the impact of a digital alert on the key patient outcomes and process outcomes

Primary outcome: in-hospital mortality within 30 days

Secondary outcome: length of stay

ICU admission

2.Methods

2.1Study design

Setting - Describe the setting, locations, and relevant dates, including periods of recruitment, exposure, follow-up, and data collection

This is a time series analysis across five NHS Trusts in England and one NHS Trust in Wales. The period of study is 1st April 2010 to 31st March 2021.

2.2 Participants - the eligibility criteria, and the sources and methods of selection of participants All adult (18+) inpatients admitted as emergency patients between 01/04/10 and 31/03/2 are initially eligible for inclusion in the study.

Intervention group: patients with a discharge diagnosis including one of the SoS sepsis codes at any place in the diagnosis.

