Control group: patients with a discharge diagnosis which is use by the NHS to identify patients with a 'Fall' code.

2.3 Variables - Clearly define all outcomes, exposures, predictors, potential confounders, and effect modifiers. Give diagnostic criteria, if applicable

Primary outcome: in-hospital mortality within 30 days of admission **Secondary**:

- In-hospital mortality within 7 days of admission
- Length of stay
- ICU admission

Intervention: Introduction of digital alerts or changes in screening programmes

Potential confounders:

- Age
- Sex
- · Comorbidities which increase the risk of poor patient outcomes
- Ethnicity
- Season

Sub-group analysis

Age-groups

Patients who are immune-compromised

2.4 Data sources/ measurement - For each variable of interest, give sources of data and details of methods of assessment (measurement).

Data are routinely collected data to comply with NHS requirements for Secondary Users Service. Data is quality checked by individual Trust before it is submitted to the NHS, and is compiled into Hospital Episode Statistics which have been widely used for research in the UK.

As part of the NIHR-Health Informatics Collaborative data managers at each trust shared data through a secure data platform. All data was quality checked and processed by the data warehouse team at ICHT.

Bias - Describe any efforts to address potential sources of bias

We are using a control intervention group to address the main source of bias – that is that for four of the six Trusts alerts were introduced at the same time as digital alerts.

Study size

Six NHS Trusts were recruited to take part in the study. The number of patients included in the study is determined by the number of patients who were discharged with an SoS ICD-10 code. The power to detect differences will be determined post-hoc.

Quantitative variables - Explain how quantitative variables were handled in the analyses. If applicable, describe which groupings were chosen and why

Ethnicity – ethnicity coding is based on recorded ethnicity using NHS ethnicity codes. Due to small groups of some ethnic groups we will combine into standard combinations for statistical comparisons. Full details of ethnic groups are included in the supplementary materials.

Age – We broke age into 10-year age groups. For statistical comparisons we combined smaller groups. Full details are included in the supplementary materials.

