Length of stay - length of stay, measured in hours, was determined from the date and time of admission and discharge recorded in the patient record. For this descriptive study we will quantify length of stay for patients who are discharged alive.

Mortality – mortality was based on discharge destination recorded. For the purposes of this study only inhospital mortality was available for all NHS trusts.

Missing data

Patient admissions will not be excluded if patient data is missing, an additional category of missing will be included for age, gender, ethnicity and deprivation. As part of quality checks we will confirm whether there are any patterns in missing data.

Statistical methods

(a) Describe all statistical methods, including those used to control for confounding

Descriptive analysis

We will describe trends in patient mix over time using graphical methods, we will use time series to determine if there were changes in patient mix, including sub-groups of patients, patients with SoS and falls patients.

We will use break point approaches to identify potential key points in time where changes occurred. This will aid in interpretation of results.

Comparative analysis

We will use interrupted time series with a control, adjusted for patient case mix and season. Each Trust will be modelled separately as the introduction of sepsis alerts and electronic health records is different for each Trust. Comparisons will be made between the change in slope and step change in counts.

(b) Describe any methods which will be used to examine subgroups and interactions

Within each model we will separately consider subgroups when we perform our analysis. We will consider a priori interactions.

(c) Explain how missing data will addressed

Missing data will be included as a category on its own for factors such as ethnicity and deprivation. We will inspect data to identify periods of missing data, and consider imputation.

ICD-10 Code	ICD-10 Description
1850	Oesophageal varices with bleeding
K226	Gastro-oesophageal laceration - haemorrhage syndrome K228 Other specified diseases of oesophagus
K250	Gastric ulcer, acute with haemorrhage
K252	Gastric ulcer, acute with both haemorrhage and perforation
K254	Gastric ulcer, chronic or unspecified with haemorrhage K256 Chronic or unspecified Gastric ulcer with both haemorrage and perforation
K260	K260 Duodenal ulcer, acute with haemorrhage
K262	K262 Duodenal ulcer, acute with both haemorrhage and perforation

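### In the four Trusts where alert and EHR started together, the controlled time series gives an alert effect only if the EHR acted equally on Suspicion of Sepsis and control patients, which the protocol neither states nor tests

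*Protocol*

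**What the plan says.** All of this is in the protocol. The impact study is the second study in the Appendix, and Section 10 points to the Appendix for the detailed statistical plans.

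- Background/rationale (1.1): "With the exception of ICHT the introduction of alerts was part of the introduction of electronic health records (EHR"). It lists the consequence openly: "The impact of the alerts on patient outcomes will be confounded by the introduction of EHRs, a major change in the hospital system".
- Same section, on ICHT: "In ICHT sepsis alerts were introduced in a phased approach".
- Same section, on concurrent changes: "A control is an appropriate method to take this type of confounding into account". The control condition is defended thus: "This is a suitable control as we would not expect these patients to trigger a sepsis alert". It adds that labelling a patient as septic should not alter control patients' outcomes.
- Bias paragraph (under 2.4): "We are using a control intervention group to address the main source of bias", the bias being that "for four of the six Trusts alerts were introduced at the same time as digital alerts".
- Comparative analysis: an interrupted time series with a control, adjusted for case mix and season, fitted separately in each Trust. "Comparisons will be made between the change in slope and step change in counts".

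Objective 2.4 asks for the impact of a digital alert. Objective 4.1 then seeks the alert that works best, and WS4 draws on the WS2 results to do so.

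**The concern.** The Bias sentence as printed says that alerts were introduced together with alerts. Read against 1.1, the second term must be EHRs: five English Trusts less ICHT gives the same four.

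The substantive problem is the assumption behind the remedy. For a control to correct for a simultaneous EHR start, two things must hold: control patients are untouched by the alert, and the EHR changes outcomes by the same proportion in SoS and control patients. The protocol argues only the first. The second is not stated, justified or tested. Because each Trust is modelled alone, no comparison between Trusts can supply it.

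At stake is what the four estimates mean. Any EHR effect peculiar to patients with infection would be published as an alert effect under objective 2.4 and carried into the WS4 judgement about which alert is best.

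**Working it through.** The protocol states no sample size, power or effect assumption for this study, so there is no figure to reproduce. The check is whether the alert effect can be identified, and what passes into the estimate if it cannot.

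**Inputs from the protocol.** Study period April 2010 to March 2021: 11 years × 12 = 132 months. Two series per Trust (SoS and control). Step and slope change. Four Trusts with a joint start. One effect size, used only for scale: a 23% lower 30-day death risk at ICHT, a ratio of 1 − 0.23 = 0.77.

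**Assumed, because the protocol gives none.** The size of any EHR effect, and a 24-month gap for the separate-dates comparison.

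**Step 1: identifiability.** Let g = 1 for SoS and 0 for control. Let E(t) and A(t) be 0 before and 1 after EHR and alert go-live, at months T_E and T_A:

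log rate = a + b·t + c·g + d·g·t + e·E + f·E·(t − T_E) + g·[h·E + i·E·(t − T_E)] + g·[j·A + k·A·(t − T_A)]

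This has 10 parameters. Here e and f are the EHR effect common to both groups, h and i the extra EHR effect in SoS patients, and j and k the alert effect.

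- T_E = T_A: the j column equals the h column and the k column equals the i column. Rank = 10 − 2 = 8. Only h + j and i + k can be estimated.
- T_A = T_E + 24 months: rank 10 of 10. The two effects separate.

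**Step 2: what the controlled estimate contains.** With a common EHR ratio C, an extra EHR ratio D in SoS patients and an alert ratio R:

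reported ratio = (C × D × R) / C = D × R

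C cancels. With C = 0.90 and D = 1, the reported ratio is 1.00 when R = 1.00 and 0.77 when R = 0.77. D passes through in full:

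| Extra EHR ratio in SoS (D) | Reported if R = 1.00 | Reported if R = 0.77 |
|---|---|---|
| 0.85 | 0.85 | 0.655 |
| 0.90 | 0.90 | 0.693 |
| 0.95 | 0.95 | 0.732 |
| 0.97 | 0.97 | 0.747 |
| 1.05 | 1.05 | 0.809 |

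The last row shows that the distortion can also run against the alert.

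**Step 3: what the estimate should be called.** Suppose the alert does nothing and the EHR ratio is 0.90 in SoS patients and 0.97 in controls. The controlled series reports 0.90 / 0.97 = 0.93. The full effect of the joint go-live on SoS patients is 0.90. So the controlled estimate is neither the alert effect (1.00) nor the whole effect of EHR plus alert (0.90). It is the joint effect in SoS patients relative to the change in controls.

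**The case against.** The protocol does not hide the problem. It says the alert's impact will be confounded by the EHR, and its verbs are modest: the control is there to address the bias and take it into account. A reader might infer that the protocol claims the control removes the bias. It does not say so. Nor is the control idle: control patients also receive the EHR, and Step 2 confirms that the shared effect cancels.

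The protocol also does not show that the EHR acts differently on infection patients. The nearest it comes is saying that detailed microbiology and antibiotic-administration data are unavailable before the EHR. That makes an infection-specific effect plausible but says nothing of its size.

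Two further readings are tempting and unsupported. One is that the training and treatment plans accompanying alerts contaminate the estimate. The Background treats them as potential mediators and objective 4.4 plans a mediation analysis, so they belong to the effect of introducing an alert. The other is that ICHT's phased roll-out will bias its result through a single step date. No such date is specified, WS2 ties the plans to each Trust's implementation approach, and coding a roll-out is analysis-plan detail.

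All of that stands and narrows the point. What it does not answer is that the one assumption needed for an alert interpretation is missing, and that with coincident dates a later analysis plan using the same per-Trust series cannot separate the effects.

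**Conclusion.** The point holds for four Trusts. There, the controlled series estimates the effect of a joint EHR-and-alert go-live on SoS patients over and above the change in controls. It equals the alert effect only if the EHR changed outcomes equally in both groups, and the protocol's case for the control does not reach that assumption. The size and direction of any error are unknown: the documents fix neither, and the ratios above are illustrations. What is certain is that the error passes through in full.

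This rests on reading the garbled Bias sentence as referring to EHRs, on alert and EHR sharing a start date in those Trusts as 1.1 implies, and on control patients being unaffected by the alert. If controls responded too, a second error would be added: with a true ratio of 0.77, a control response of 0.95 or 0.90 gives 0.77 / 0.95 = 0.81 or 0.77 / 0.90 = 0.86.

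**What to change.** 1. Bias paragraph: correct the sentence so that the second term reads as EHRs. Replace the claim with a statement that the control removes only the EHR effect common to SoS and control patients. Name one control condition when doing so, because the impact study gives gastrointestinal bleeding in one place and falls in another.
2. For the four joint-start Trusts, define and report the estimate as the effect of the joint EHR-and-alert go-live on SoS patients over and above the change in controls. State that it reads as an alert effect only under an equal EHR effect in the two groups. It should not be labelled the full effect of introducing an EHR with an alert (Step 3).
3. Base alert-specific claims on ICHT, where the alert was introduced separately from the EHR. Add a separate EHR interruption if ICHT's EHR go-live falls within April 2010 to March 2021.
4. In WS4, do not treat the four joint estimates as evidence on the alert alone.

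The cost is wording, possibly one extra interruption in the ICHT model, and obtaining ICHT's EHR go-live date. Objective 1.2 covers the introduction of alerts, and the protocol does not say that EHR dates are collected. The downside is a narrower claim in four Trusts.

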We will determine the association between the alert and completion of individual process measures, completion of the three measures, and whether the associations are different for different patient subgroups.

We will model each Trust separately and also model all patients in a multi-level model with clustering at Trust level. We will determine the sensitivity of results to the modelling approach.

Association between alerting and patient outcomes

We will assess the association between alerting and patient outcomes using a competing risks survival analysis with discharge and death as competing risks. This will allow us to fully adjust for patient factors and consider both patients who survive to discharge and those who do not. We will include process measure completion as time varying covariates.

In addition, we will separately model ICU admission after alerting using both a survival analysis and logistic model.

Association between alerting and coding

We will describe the coding of alerting patients between Trusts. The Trust which does not have a sepsis specific alert will be excluded. We determine if the differences are significant using chi-squared test. We will use descriptive approaches to compare sepsis coding between Trusts in patients with a SoS code. We will also consider whether the patterns are the same across the main patient subgroups. Statistical significance will be assessed using chi-squared tests.

(b) Methods used to examine subgroups and interactions

Within each model we will separately consider subgroups when we perform our analysis. We will consider a priori interactions.

(c) Missing data

Missing data will be included as a category on its own for factors such as ethnicity and deprivation. We will inspect data to identify periods of missing data which may be a result of EHR downtime, if necessary we will consider imputation.

We will ensure from clinicians that all process outcomes are likely to be recorded in the EHR and policy for carrying out the processes are the same across all Trusts.

Bibliography

[2] NHS Bed Availability and Occupancy Data – Overnight. Available from:

https://www.england.nhs.uk/statistics/statistical-work-areas/bed-availability-and-occupancy/bed-data-overnight/

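### The impact study measures length of stay, a secondary outcome, only in patients discharged alive. This conditions on survival and distorts the before/after comparison if the alert changes mortality.

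*Protocol*

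**What the plan says.** The protocol's appendix holds two study plans, one descriptive and one on the impact of the alert. Section 10 points to the appendix for the detailed statistical plans, so these definitions are the stated plan for WorkStream 2.

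In the impact study:

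- The Objective paragraph gives "Secondary outcome: length of stay", and section 2.3 (Variables) lists it again as secondary.
- The primary outcome in section 2.3 is "in-hospital mortality within 30 days of admission".
- Under Quantitative variables, length of stay is defined in hours from admission to discharge, with the restriction "For this descriptive study we will quantify length of stay for patients who are discharged alive". No other definition is given.
- Under Comparative analysis: "We will use interrupted time series with a control, adjusted for patient case mix and season". Each Trust is modelled separately. Death is not treated as a competing event for discharge.

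In the descriptive study, section 2.7 (Quantitative variables) carries the same length-of-stay sentence. That study's outcome analysis, however, plans a "competing risks survival analysis with discharge and death as competing risks", so that patients who die are considered as well as those who go home. The impact study has no counterpart.

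**The concern.** A survivors-only stay is a common entry in a descriptive table. In the impact study, the same quantity is compared before and after an intervention meant to change who survives. The restriction removes patients who die in hospital, nearly the same group that counts as events for the primary outcome; the only difference is in-hospital deaths after day 30. If mortality changes at the introduction of the alert, the set of patients whose stay is counted changes at the same moment. A step in mean stay then mixes a change in how long patients stay with a change in which patients are counted.

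Nothing else in the impact study separates the two:

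- The listed confounders are age, sex, comorbidities, ethnicity and season. Acute severity, which would distinguish the additional survivors from the rest, is not among them.
- The control series is chosen because its outcomes should not respond to sepsis being identified. It is therefore not expected to share an alert-driven change in survivor mix, and subtracting it does not remove the artefact.

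Section 7.2 describes length of stay as an indicator of patient experience and a key hospital target, so even a shift of a few percent in either direction would be read as a finding.

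**Working it through.** The protocol gives no length-of-stay figure, baseline mortality or advance power calculation for the impact study ("The power to detect differences will be determined post-hoc"), so there is no planned figure to reproduce. The check asks how far mean survivor stay moves when the alert has no true effect on anyone's stay.

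**Inputs**

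- Risk ratio for death 0.77, from the background section of the impact study: "In ICHT the introduction of digital sepsis alerts was associated with a 23% lower risk of death within 30 days".
- Baseline in-hospital mortality m0: assumed 5%, 10% and 20%.
- Ratio r of the mean stay of saved patients to that of patients who survive either way: assumed 1.5 to 2.5, with 1 and 0.75 to test the sign.
- Mean stay of patients who survive either way, for conversion to days: assumed 8 days, so r of 1.5 to 2.5 means 12 to 20 days.

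**Formulae**

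- Mortality after the alert: m1 = 0.77 × m0.
- Share of post-alert survivors who are saved patients: w = (m0 − m1)/(1 − m1).
- Relative change in mean survivor stay: w × (r − 1).

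**Results**

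| m0 | w | r = 0.75 | r = 1 | r = 1.5 | r = 2.5 |
|---|---|---|---|---|---|
| 5% | 0.0115/0.9615 = 1.20% | −0.3% | 0 | +0.6% (0.05 days) | +1.8% (0.14 days) |
| 10% | 0.023/0.923 = 2.49% | −0.6% | 0 | +1.2% (0.10 days) | +3.7% (0.30 days) |
| 20% | 0.046/0.846 = 5.44% | −1.4% | 0 | +2.7% (0.22 days) | +8.2% (0.65 days) |

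Direct check at m0 = 10% and r = 2.5: (0.90 × 8 + 0.023 × 20)/0.923 = 7.66/0.923 = 8.30 days, against 8.00 before.

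**How much true benefit this could hide.** A true shortening of x in all survivors is exactly cancelled when (1 − x)(1 + w(r − 1)) = 1, so x = w(r − 1)/(1 + w(r − 1)). At r = 2 this gives 1.2%, 2.4% and 5.2% for baseline mortality of 5%, 10% and 20%. A smaller true reduction would show as an increase.

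**Simulation of the sign.** Four million admissions were simulated with log-normal stays, severity raising the risk of death, and mortality falling from about 10.5% to 8.1%. Mean survivor stay changed by +1.5% when sicker patients stay longer, by 0 when severity and stay are unrelated, and by −0.4% when sicker patients stay for a shorter time.

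**The case against.** A reader might infer that an alert that saves lives will necessarily appear to lengthen stay, or that the comparison runs against benefit whenever mortality improves. The protocol does not support that. The sign depends on whether saved patients stay longer than other survivors, and it gives no figure on this. Apparent lengthening also requires the artefact to exceed any true shortening.

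The 23% comes from one Trust with a phased introduction and a propensity-weighted analysis. The impact study covers six Trusts and emergency admissions with a Suspicion of Sepsis code in any diagnostic position. A smaller mortality effect gives a smaller artefact. These limits on direction and size stand.

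It can also be said that the sentence limits itself to a descriptive study and may have been copied from section 2.7 of the descriptive plan. The impact study has separate descriptive and comparative headings, and its comparative paragraph does not mention survivors. The copying is likely, and it means that application of the rule to the time series is the natural reading rather than an explicit statement. But no other definition is offered for this secondary outcome, so the text needs correcting on either reading.

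Finally, adjustment for age and comorbidity may absorb part of a shift in survivor mix, and mortality at 7 and 30 days is reported in the same study, so a careful reader could set the two side by side. Both soften the problem. Neither removes it, because acute severity is not among the listed covariates and the length-of-stay estimate itself would remain uncorrected.

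**Conclusion.** The point holds as a conditional one. The impact study's only definition of length of stay conditions on survival, essentially its primary outcome, and the planned analysis does not correct for this. If the alert changes mortality, the before/after comparison of stay is distorted.

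The distortion is towards longer stay if saved patients stay longer than other survivors, and it can then mask or reverse a true reduction. It is zero if the stays are equal and slightly negative if they are shorter. Its size is about 0.6–8% across baseline mortality of 5–20% and a stay ratio of 1.5–2.5, and about 1.2–3.7% at 10% mortality. Apart from the cited 23% reduction, every input to that range is an assumption, and the 23% is itself a single-Trust figure.

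The effect is modest and confined to one secondary outcome, but the plan should be changed before analysis because the correction is cheap. That the result would be misread as a harm of the alert is possible, but nothing in the protocol establishes it.

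**What to change.** In the impact study:

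1. Define length of stay over all admissions with in-hospital death as a competing event. A form that suits the controlled interrupted time series is the proportion of all admissions discharged alive by fixed days, for example 7 and 30, the time points already used there for mortality.
2. Keep stay among live discharges as a descriptive entry, reported beside mortality for the same period.
3. Delete the opening phrase of the length-of-stay sentence that calls this a descriptive study.

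Days alive and out of hospital should not be used. It needs deaths after discharge, and the impact study's mortality definition states that only in-hospital deaths are available for all Trusts, so patients who died after discharge would be counted as alive.

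The change needs only admission and discharge times and discharge destination, which the study already holds. The cost is protocol wording, some extra analysis code and a summary slightly less familiar than mean stay. The proportion discharged alive rises both with quicker discharge and with fewer deaths, so it must be read next to the mortality result.
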